5.2 Common Eligibility Criteria for all Sub-Studies

a. **Disease Related Criteria**

1. Patients must not have EGFR sensitizing mutations, EGFR T790M mutation, ALK gene fusion, ROS 1 gene rearrangement, and BRAF V600E mutation unless they have progressed following all standard of care targeted therapy.
2. Patients must not have documented evidence of acute hepatitis or have an active or uncontrolled infection.
3. Patients with a known history of HIV seropositivity:
  - i. Must have undetectable viral load using standard HIV assays in clinical practice.
  - ii. Must have CD4 count  $\geq 400/\text{mcL}$ .
  - iii. Must not require prophylaxis for any opportunistic infections (i.e., fungal, mAC, or PCP prophylaxis).

- iv. Must not be newly diagnosed within 12 months prior to sub-study registration.

b. **Prior/Concurrent Therapy Criteria**

- 1. Patients must have progressed (in the opinion of the treating physician) following the most recent line of therapy.
- 2. Patients must not have received any prior systemic therapy (systemic chemotherapy, immunotherapy or investigational drug) within 21 days prior to sub-study registration. Patients must have recovered ( $\leq$  Grade 1) from any side effects of prior therapy. Patients must not have received any radiation therapy within 14 days prior to sub-study registration. (See [Section 5.2c.2](#) for criteria regarding therapy for CNS metastases).

c. **Clinical/Laboratory Criteria**

- 1. Patients must have measurable disease (see [S1900A Section 10.1](#)) documented by CT or MRI. The CT from a combined PET/CT may be used to document only non-measurable disease unless it is of diagnostic quality as defined in [S1900A Section 10.1c](#). Measurable disease must be assessed within 28 days prior to sub-study registration. Pleural effusions, ascites and laboratory parameters are not acceptable as the only evidence of disease. Non-measurable disease must be assessed within 42 days prior to sub-study registration. All disease must be assessed and documented on the Baseline Tumor Assessment Form. Patients whose only measurable disease is within a previous radiation therapy port must demonstrate clearly progressive disease (in the opinion of the treating investigator) prior to registration. See [S1900A Section 15.0](#) and [LUNGMAP](#) Appendix 18.2 for guidelines and submission instructions for required central radiology review. CT and MRI scans must be submitted for central review via TRIAD.
- 2. Patients must have a CT or MRI scan of the brain to evaluate for CNS disease within 42 days prior to sub-study registration. Patient must not have leptomeningeal disease, spinal cord compression or brain metastases unless: (1) metastases have been locally treated and have remained clinically controlled and asymptomatic for at least 14 days following treatment, and prior to registration, AND (2) patient has no residual neurological dysfunction and has been off corticosteroids for at least 24 hours prior to sub-study registration.
- 3. Patient must not have had a major surgery within 14 days prior to sub-study registration. Patient must have fully recovered from the effects of prior surgery in the opinion of the treating investigator.
- 4. Patients must have an ANC  $\geq$  1,500/mcl, platelet count  $\geq$  100,000 mcl, and hemoglobin  $\geq$  9 g/dL obtained within 28 days prior to sub-study registration.
- 5. Patients must have adequate hepatic function as defined by serum bilirubin  $\leq$  Institutional Upper Limit of Normal (IULN) and either ALT or AST  $\leq$  2 x IULN within 28 days prior to sub-study registration (if both ALT and AST are done, both must be  $\leq$  2 IULN). For patients with liver metastases,

bilirubin and either ALT or AST must be  $\leq 5 \times$  IULN (if both ALT and AST are done, both must be  $\leq 5 \times$  IULN).

6. Patients must have a serum creatinine  $\leq$  the IULN OR or calculated creatinine clearance  $\geq 50$  mL/min using the following Cockcroft-Gault Formula. This specimen must have been drawn and processed within 28 days prior to sub-study registration:

Calculated Creatinine Clearance =  $\frac{(140 - \text{age}) \times (\text{actual body weight in kg}\dagger)}{72 \times \text{serum creatinine}^*}$

Multiply this number by 0.85 if the patient is a female.

$\dagger$  The kilogram weight is the patient weight with an upper limit of 140% of the IBW.

$*$  Actual lab serum creatinine value with a minimum of 0.7 mg/ dL.

7. Patients must have Zubrod performance status 0-1 (see [S1900A Section 10.4](#)) documented within 28 days prior to sub-study registration.
8. Patients must not have any Grade III/IV cardiac disease as defined by the New York Heart Association Criteria (i.e., patients with cardiac disease resulting in marked limitation of physical activity or resulting in inability to carry on any physical activity without discomfort), unstable angina pectoris, and myocardial infarction within 6 months, or serious uncontrolled cardiac arrhythmia (see [S1900A Appendix 18.1](#)).
9. Pre-study history and physical exam must be obtained within 28 days prior to sub-study registration.
10. No other prior malignancy is allowed except for the following: adequately treated basal cell or squamous cell skin cancer, in situ cervical cancer, adequately treated Stage I or II cancer from which the patient is currently in complete remission, or any other cancer from which the patient has been disease free for five years.
11. Patients must not be pregnant or nursing. Women of reproductive potential must have agreed to use an effective contraceptive method during the study and 6 months after completion of study treatment. Men of reproductive potential must have agreed to use an effective contraceptive method during the study and 3 months after completion of study treatment. A woman is considered to be of "reproductive potential" if she has had menses at any time in the preceding 12 consecutive months. In addition to routine contraceptive methods, "effective contraception" also includes heterosexual celibacy and surgery intended to prevent pregnancy (or with a side-effect of pregnancy prevention) defined as a hysterectomy, bilateral oophorectomy or bilateral tubal ligation. However, if at any point a previously celibate patient chooses to become heterosexually active during the time period for use of contraceptive measures outlined in the protocol, he/she is responsible for beginning contraceptive measures during the study and for 6 months after study completion for females and 3 months after study completion for males.

### 5.3 Specimen Submission Criteria

- a. Patients must agree to have blood specimens submitted for circulating tumor DNA (ctDNA) as outlined in Section 15.0.
- b. Patients must also be offered participation in banking and in the correlative studies for collection and future use of specimens as described in [S1900A Section 15.0](#).

#### 5.4 Regulatory Criteria

- a. Patients **must** be informed of the investigational nature of this study and must sign and give written informed consent in accordance with institutional and federal guidelines.
- b. As a part of the OPEN registration process (see [S1900A Section 13.0](#) for OPEN access instructions) the treating institution's identity is provided in order to ensure that the current (within 365 days) date of institutional review board approval for this study has been entered in the system.
- c. Patients with impaired decision-making capacity are eligible as long as their neurological or psychological condition does not preclude their safe participation in the study (e.g., tracking pill consumption and reporting adverse events to the investigator).

### 6.0 STRATIFICATION FACTORS

Patients will be stratified into two cohorts based on their histology.

Cohort 1: Patients with squamous cell lung cancer.

Cohort 2: Patients with non-squamous cell lung cancer (adenocarcinoma, large cell, NSCLC NOS, mixed histology with any non-squamous component).

#### 7.1 Disease Assessment

See [Section 9.0](#) for disease assessment time points. Submit scans as outlined in [Section 14.0](#) and [Section 15.0](#).

##### Disease Assessment During Treatment

CT or MRI (the same method used at pre-study to meet the eligibility criteria in [Section 5.2](#)) must be repeated every 6 weeks ( $\pm$  7 day window), for the first year regardless of treatment delays, then every 12 weeks ( $\pm$  7 day window) until disease progression and discontinuation of protocol treatment. The 6 weeks should start from Cycle 1 Day 1.

Pre-study Brain CT/MRI is required 42 days prior to sub-study registration per [Section 5.2](#). If patient has brain metastases at baseline, scans must use the same modality as baseline and be repeated every 12 weeks ( $\pm$  7 day window) regardless of treatment delays, while on treatment.

**Disease Assessment During Off Protocol Treatment, Prior to Progression**

After off protocol treatment prior to progression, disease assessments must continue every 12 weeks ( $\pm$  7 day window) until progression.

If patient has brain metastases at baseline, continue brain CT or MRI scans (same modality as baseline) after off protocol treatment prior to progression, as clinically indicated. For alignment with the protocol and good clinical practice, recommended frequency of brain scans after off protocol treatment (and prior to progression) is at least every 12 weeks, unless more frequent scans are clinically appropriate.

**7.2 Precautions**

**Photosensitivity**

Patients should use common precautions when going outside, such as applying sunscreen and/or covering exposed skin with clothing and wearing a hat and sunglasses, as photosensitivity has been observed.

**Concomitant Medications**

Use caution for concomitant medications that are substrates of CYP1A2, CYP2C9, CYP2C19 and/or CYP3A, and adjust dosage if clinically indicated. If co-administration with warfarin (a CYP2C9 substrate) cannot be avoided, consider increasing the frequency of international normalized ratio (INR) monitoring. Although in vitro rucaparib metabolism mediated by CYP3A4 was slow, a significant contribution of CYP3A4 in vivo cannot be excluded. Caution should be used for concomitant use of strong CYP3A4 inhibitors or inducers. Selection of an alternative concomitant medication is recommended.

Because rucaparib is a strong BCRP inhibitor, concomitant use of drugs that are BCRP substrates (e.g., rosuvastatin) are **not allowed** during the treatment study. See the following url for examples:

<https://www.fda.gov/Drugs/DevelopmentApprovalProcess/DevelopmentResources/DrugInteractionsLabeling/ucm093664.htm#table5-2>

See [Section 3.0](#) and [Appendix 18.5](#) for additional details.

**Myelodysplastic Syndrome/Acute Myeloid Leukemia (MDS/AML)**

MDS/AML occurred in patients exposed to rucaparib, including one fatal event of AML. Monitor patients for hematological toxicity at baseline and monthly thereafter. Discontinue if MDS/AML is confirmed.

If AML/MDS is suspected, then patient should be referred to a hematologist and analysis of the bone marrow with cytogenetic studies are recommended according to standard hematologic practice. Bone marrow analysis should include a bone marrow aspirate per standard hematologic practice.

Please see [Section 8.3](#) for additional guidance on neutropenia, thrombocytopenia and anemia toxicities.

**Embryo-Fetal Toxicity**

Rucaparib can cause fetal harm. Advise females of reproductive potential of the potential risk to a fetus and to use effective contraception.

**7.3 Pre-Medication**

- a. Pre-medication associated with standard drug administration and supportive care (including anti-diarrheals, antibiotics, diuretics or other medications) may be given as indicated by the current American Society of Clinical Oncology (ASCO) guidelines.

7.4 Treatment – **S1900A**

Agent	Dose	Route	Day	Schedule
Rucaparib	600 mg**	Oral	BID	Continuous

\* Note: One cycle = 21 calendar days

\*\* Total daily dose = 1200mg

Site and patient instructions can be found in the Intake Calendar ([Section 18.6](#)).

7.5 Drug Compliance Documentation

Drug compliance for rucaparib will be recorded by patients in the Intake Calendar (see [www.ctsu.org](http://www.ctsu.org)). Institutional CRAs will review and ascertain patient adherence with protocol therapy at the end of treatment for each cycle. Calendar should be kept in the patient's clinic chart. Sites utilizing the CIRB must use the Intake Calendar provided.

7.6 Criteria for Removal from Protocol Treatment

- a. Progression of disease or symptomatic deterioration (as defined in [Sections 10.2d](#) and [10.2e](#)). \*

\* Upon progression, the Request for New Sub-Study Assignment Form may be submitted under the patient's screening protocol ([LUNGMAP](#) or [S1400](#)) to receive a new sub-study assignment (see [Section 14.4i](#)).

- b. Unacceptable toxicity.
- c. Treatment delay for any reason > 28 days (or as noted in [Section 8.0](#)).
- d. The patients may withdraw from the protocol treatment at any time for any reason.

7.7 Discontinuation of Treatment

All reasons for discontinuation of treatment must be documented in the Off Treatment Notice.

7.8 Follow-Up Period

All patients will be followed until death or 3 years after sub-study registration, whichever occurs first.

Note: Patients who enroll on a new sub-study following progression must continue follow-up on this sub-study, in addition to follow-up on the new sub-study.

**8.0 TOXICITIES TO BE MONITORED AND DOSE MODIFICATIONS**

8.1 NCI Common Terminology Criteria for Adverse Events

This study will utilize the CTCAE (NCI Common Terminology Criteria for Adverse Events) Version 5.0 for toxicity and Serious Adverse Event reporting. A copy of the CTCAE Version 5.0 can be downloaded from the CTEP home page (<http://ctep.cancer.gov>). All appropriate treatment areas should have access to a copy of the CTCAE Version 5.0.

## 8.2 General Considerations

- a. Missed doses are to be omitted rather than made up.
- b. If multiple toxicities are experienced, dose modifications will be based on the toxicity requiring the largest dose reduction.
- c. Once dose is reduced, patients will continue at the new dose. No dose re-escalations are allowed.
- d. A maximum of three dose reductions are allowed.
- e. The maximum dose delay for any reason is 28 days.

See [Section 7.3](#) for patient instructions.

## 8.3 Dose Modifications – Rucaparib

Dose modifications should be made based on the observed toxicity, as summarized in the tables below.

DRUG	DOSE LEVEL	DOSE
Rucaparib	Full	600 mg BID
	-1 Level	500 mg BID
	-2 Level	400 mg BID
	-3 Level	300 mg BID
	-4 Level	Discontinue

As discussed above, the most common side effects of rucaparib treatment include gastrointestinal disorders (nausea, vomiting, diarrhea, and constipation), asthenia/fatigue, clinical chemistry elevations (ALT/AST, creatinine, and cholesterol), myelosuppression (decreases in hemoglobin, lymphocytes, platelets, and neutrophils), dysgeusia, and decreased appetite. Modification of rucaparib dose may be a necessary component of AE management, and study specific protocol guidelines for dose modifications should be followed. Dose interruptions, with or without subsequent dose reductions, may help to ameliorate AEs attributed to rucaparib therapy.

Treatment with rucaparib should be held if any of the following are observed and a dose reduction should be considered or implemented.

- Grade 3 or 4 hematologic toxicity (except for lymphocyte count decrease).
- Grade 3 or 4 non-hematologic toxicity (except for alopecia, nausea, vomiting, or diarrhea adequately controlled with systemic antiemetic/antidiarrheal medication administered in standard doses according to the study center routines). Grade 3 or Grade 4 ALT/AST elevations should be managed as described below ([Table 2](#)).
- In addition, and at the discretion of the investigator, the dose of rucaparib may be held and/or reduced for Grade 2 toxicity not adequately controlled by concomitant medications and/or supportive care.

**Table 1: Bone Marrow Suppression Dose Modifications/Interruptions**

Toxicity	Dose Modification/Interruption	Toxicity Management
Anemia		
≥ Grade 3	Hold protocol therapy until resolution to ≤ Grade 2. May resume protocol therapy at next lower dose.  If dose interruption is >28 consecutive days, permanently discontinue protocol therapy.	If persists >14 consecutive days, or a dependence upon blood transfusion occurs, then complete weekly blood counts until resolution.*
Neutropenia		
≥ Grade 3	Hold rucaparib until resolution to ≤ Grade 2 and resume at lower dose.	For patients with persistent neutropenia that does not stabilize or recover with dose modification, consider additional diagnostic evaluation, including bone marrow examination.*
Thrombocytopenia		
≥ Grade 3	Evaluate for other medications that may induce thrombocytopenia and discontinue/modify these medications if indicated in the opinion of the investigator. Hold rucaparib until resolution to ≤ Grade 1 and resume at lower dose.	For patients with persistent thrombocytopenia that does not stabilize or recover with dose modification, consider additional diagnostic evaluation, including bone marrow examination.*

\* If a Grade ≥ 3 anemia, neutropenia, or thrombocytopenia occurs and after 28 days of interruption of rucaparib, these cytopenias have not improved to CTCAE Grade ≤ 2, then patient should be referred to a hematologist and analysis of the bone marrow with cytogenetic studies are recommended according to standard hematologic practice. Bone marrow analysis should include a bone marrow aspirate per standard hematologic practice.

**Table 2: ALT/AST Elevations Dose Modifications/Interruptions**

Toxicity	Dose Modification/Interruption	Toxicity Management
Grade 3	
Hold protocol therapy until resolution to <math>\leq</math> Grade 2. Monitor liver function tests. If resolves to <math>\leq</math> Grade 2 within 2 weeks, continue protocol therapy at same dose.
 
If persists beyond 2 weeks or bilirubin or alkaline phosphatase is elevated, hold protocol therapy until <math>\leq</math> Grade 2 and resume at dose reduction.
 
If elevation returns on a second occasion, reduce dose.
 
See Section 2.3 (Overview of Safety) for information on transient elevation that can occur in the first 2-3 weeks.
	
In the absence of other signs of liver dysfunction:
 
 
Monitor liver function tests weekly until resolution to <math>\leq</math> Grade 2.
 
Continuation of protocol therapy with elevation of ALT/AST up to Grade 3 is allowed provided bilirubin is <math><</math> ULN and alkaline phosphatase is <math>< 3 \times</math> ULN.
 

Grade 4	Hold protocol therapy until values have returned to $\leq$ Grade 2 or better, then resume rucaparib with a dose reduction.	Monitor liver function tests weekly for 3 weeks after rucaparib has been restarted.

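### Table 2, Grade 3 ALT/AST row: the alkaline phosphatase trigger for hold-and-reduce has no stated limit and can overlap the condition for continuing treatment

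*Combined protocol and SAP*

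**What the plan says.** Section 8.3 sends these events to Table 2: "Grade 3 or Grade 4 ALT/AST elevations should be managed as described below". The Grade 3 row of Table 2 has two cells.

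**Dose-modification cell.** It opens with a hold until Grade 2 or lower and states no exception. It then separates two outcomes. The first is "Grade 2 within 2 weeks, continue protocol therapy at same dose". The second is "If persists beyond 2 weeks or bilirubin or alkaline phosphatase is elevated, hold protocol therapy until" Grade 2 or lower, followed by resumption at a reduced dose. No multiple of ULN is attached to 'elevated'. A return of the elevation on a second occasion leads to a dose reduction.

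**Toxicity-management cell.** Its lead-in is "In the absence of other signs of liver dysfunction". Under it stand weekly liver tests and the permission "Continuation of protocol therapy with elevation of ALT/AST up to Grade 3 is allowed provided bilirubin is" below ULN, with the further condition "ULN and alkaline phosphatase is" below 3 x ULN.

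Neither cell refers to the other. Section 8.2 adds two general rules that bear on the consequence: "Once dose is reduced, patients will continue at the new dose. No dose re-escalations are allowed" and "Missed doses are to be omitted rather than made up".

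**The concern.** The two cells test the same analyte against different wording. One uses an undefined word and the other a number. A site that reads the first cell may hold and then reduce. A site that reads the second may continue at the current dose. Both would be following the table as printed, for the same laboratory values.

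The situation is foreseeable. ALT/AST increase is among the commonest Grade 3 or higher events in Section 2.3. Raised alkaline phosphatase is itself a listed rucaparib event in Section 3.1c (the 4 to 20% column), and the Section 9.1 calendar tests it before study and at each cycle. The hepatic eligibility criterion in Section 5.2c limits bilirubin and ALT/AST but sets no limit for alkaline phosphatase, so a patient could enter the study already above ULN.

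At stake is consistent handling of a liver safety signal across sites, and on one reading a dose cut that the protocol does not allow to be undone.

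**Working it through.** The plan gives no figure to reproduce here. The check compares the two conditions over the range of alkaline phosphatase (ALP) and then works out the dose difference.

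**Assumptions.** First occurrence of Grade 3 ALT/AST; bilirubin below ULN; no other sign of liver dysfunction; 'elevated' read as above ULN; a dose reduction taken as one level.

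**Step 1: compare the conditions.**

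| ALP | Dose-modification cell | Toxicity-management cell |
|---|---|---|
| At or below ULN | Hold; same dose if resolved within 2 weeks | Continuation allowed |
| Above ULN, below 3 x ULN | Hold, then reduced dose | Continuation allowed |
| 3 x ULN or more | Hold, then reduced dose | Continuation not allowed |

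The middle band is the overlap. For example, Grade 3 ALT with bilirubin 0.8 x ULN and ALP 2 x ULN meets both rules. In the bottom band the cells agree. In the top band they differ only on whether a hold is needed.

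**Step 2: test other readings of the words.**

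- *'Elevated' means failing the continuation condition.* The overlap disappears. But the one word must then mean ULN or more for bilirubin and 3 x ULN or more for ALP, and the text states neither limit.
- *ALP above ULN counts as an other sign of liver dysfunction.* Continuation is then excluded by the lead-in. But the 3 x ULN limit would have no function, because every value between ULN and 3 x ULN would already be excluded.

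**Step 3: look for text that settles it.** The body of Section 8.3 refers to Table 2. Calendar footnote 3 in Section 9.1 repeats the weekly monitoring and refers back to Table 2. Section 2.3, which Table 2 cites, gives background and no rule. Section 8.2b ranks several toxicities against each other, not two instructions for one toxicity. None of these links the two cells or defines 'elevated'.

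**Step 4: size in the overlap band.** Section 7.4 gives 600 mg BID = 1200 mg/day. The Section 8.3 dose table gives level -1 as 500 mg BID = 1000 mg/day.

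(1200 - 1000) / 1200 = 16.7% lower after the hold, with no re-escalation.

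This figure applies at full dose only. From level -1 the step is (1000 - 800) / 1000 = 20%; from level -2 it is (800 - 600) / 800 = 25%; below level -3 the dose table's next entry is discontinuation.

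**Step 5: size in the top band.** The dose level is the same on both paths if the event resolves within 2 weeks. The difference is an interruption of at most 14 days: 14 x 2 = 28 doses out of 21 x 2 = 42 in a cycle, or 66.7%. This is the ceiling of the same-dose branch, not an expected loss.

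**The case against.** The strongest case on the other side has four parts.

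**Default and exception.** The second cell is a conditional permission, not an order. A general hold beside a permission limited by liver findings reads naturally as a rule with an exception. Section 8.3 also sends ALT/AST to Table 2 from the bullet that lists exceptions to the general Grade 3 or 4 hold, which supports treating the table as a special regime. This largely stands. The hold-versus-continue question is therefore only a supporting point: the exception is probably intended but is not marked.

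**No impossible instruction.** A reader might infer that the cells give contradictory orders, so that a site must breach one of them. The documents do not support that. A site that holds and reduces obeys the order and does not breach a permission. What remains is that another site may continue on the same values.

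**Dependence on one word.** The overlap needs 'elevated' to mean above ULN. This stands as a limit on the finding. The alternative reading removes the overlap only by supplying two limits that the table does not state.

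**Mitigation.** Section 2.3 reports, in ovarian cancer patients, that the transient ALT/AST elevations were not accompanied by abnormal bilirubin increases, generally resolved, and led few patients to discontinue. Alkaline phosphatase is not mentioned there. The contact page lists a contact for treatment and toxicity questions, and the contents list a Section 8.4 on dose modification contacts (its text is not in the copy reviewed and is not counted as a gap). A contact can settle single cases but does not change the table.

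**Conclusion.** The point holds in a narrow form. Within the Grade 3 row of Table 2, the ALP trigger for hold-and-reduce has no limit, while the condition for continuing has one at 3 x ULN. On the assumption that 'elevated' means above ULN, values between ULN and 3 x ULN with bilirubin below ULN meet both. At full dose the paths differ by 200 mg/day (16.7%) after a hold, and the reduction is permanent. No visible text resolves this.

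Two stronger conclusions are tempting and should not be drawn. First, the frequency bands in Section 3.1c might seem to give a count of affected patients. They state neither grade nor joint occurrence, so they say nothing about Grade 3 ALT/AST together with ALP in the overlap band, and the number cannot be computed. Second, a reader might infer damage to the primary analysis. No response-rate design figure, endpoint or decision rule depends on this row.

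The severity is minor. It is still worth correcting, because it concerns a stated safety rule and the correction is cheap.

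**What to change.** The sponsor's clinical and safety team should reconcile the two Grade 3 cells of Table 2 by stating how the hold and the permission to continue relate. They should also reconcile the two ALP statements, including what 'elevated' means, so that one set of laboratory values leads to one instruction. Which rule and which limit apply is the sponsor's choice; this review takes no position on it.

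The cost is a table clarification by amendment and a notice to sites. There is no statistical cost: sample size, analyses and decision rules stay as they are.
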